***Sample size calculation***

Between 24 and 28 patients will be included in the study.

The sample size calculation is based on the fact that:

- with a group of 20 evaluable patients the study group is large enough to give an answer whether sentinel node(s) can be detected related to the ovarian lymphatic flow when the tracers are injected in the ovarian ligaments. For this purpose both patients with an ovarian and endometrial malignancy, planned for a staging laparotomy can and will be included.
- patients with a benign result on frozen section of the suspicious ovary will be excluded from the study because no lymph node(s) will be resected in these patients. These patients will be documented and described in the report after the study.
- based on retrospective data, in 60% of the patients with a suspicious ovary, frozen section will confirm a ovarian malignancy.
- to calculate one of the secondary endpoints (incidence of false negative sentinel lymph node) at least 10 patients with ovarian cancer should be part of the 20 evaluable patients.

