### **3. STUDY DESIGN**

Observational feasibility study to detect sentinel nodes: mapping the lymphatic drainage of the ovaries.

The study will end after 20 patients, of which at least 10 patients with ovarian cancer, are included in which the complete sentinel node procedure has been performed. The expected inclusion period is estimated to be two years. If the detection rate of the sentinel node is less than 50%, or when less 5 patients are included in a year, the study will end prematurely.

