### **Surgical procedures**

#### *Patients with a high suspicion of a malignant ovarian tumour*

After making the median incision and opening the abdomen, before starting with removal of the enlarged and suspicious adnex, blue dye and the radioactive isotope will be injected in the ligamentum ovarii proprium (median side) and the ligamentum infundibulo-pelvicum (lateral side), close to the ovary and just below the peritoneum. Four syringes will be made containing 0.2 ml patent blue and 0.15 ml (20-MBq) radioactive isotope (99mTc-nanocolloid or Nanocoll®, GE Healthcare, Eindhoven, The Netherlands, see appendix for information leaflet) will be given. Mixing patent blue and radioactive isotope does not affects the quality of the two substances, nor does it give extra or different side effects for the patient [36]. The

99mTc-nanocolloid is prepared by trained laboratory staff on the nuclear lab in a sterile 'class A' Laminar Air Flow (LAF) hood. Afterwards patent blue is added and the syringe is mixed. This is done 30 minutes before the start of the surgery.

A 15-minute interval will be planned after injection. The exact time interval for detection of positive nodes is unclear. Common practice is to wait for 15 minutes, if in this time period the node is not detected, it is considered negative. In daily practice a wait of more than 15 minutes during surgery is not workable. At 5 and 10 minutes the radioactivity will be measured along the lymphatic tract to document whether or not perhaps sentinel node(s) can be identified at a shorter time-interval in future studies. A Geiger counter measures the radioactivity. The Geiger counter will be the same device in all surgeries.

After the 15 minutes time-interval the adnex will be removed and admitted to the pathologist for a frozen section. If the result is benign, no further actions will be performed in these patients. If the result is malignant, the sentinel node(s) will be identified either (once more) by the radioactive tracer and / or visually (blue dye) after opening the retroperitoneal space.

After removal of the sentinel node(s) a complete standard staging procedure will be performed including a comprehensive at random sampling of other lymph nodes at the different locations.

Surgical steps related to the study (standard or extra):

- Median laparotomy (standard care)
- Injection of blue dye and radioactive isotope (extra for the study)
- 15 minute waiting time during the surgery (extra for the study)

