#### ***Withdrawal of individual subjects and replacement***

Subjects can leave the study at any time for any reason if they wish to do so without any consequences. The investigator can decide to withdraw a subject from the study for urgent medical reasons. Also patients with an ovarian tumour and benign result at frozen section during surgery will be excluded from the study.

These patients will be replaced by a new study subject until 20 completed sentinel node procedures are performed.

[figure not shown]

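### The planned 24 to 28 inclusions do not follow from the protocol's own 60% malignancy rate, and the assumed ovarian/endometrial mix is not stated

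*Protocol*

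**What the plan says.** The Protocol, section 4, Sample size calculation, opens with the total: "Between 24 and 28 patients will be included in the study". It then lists the facts on which that number rests:

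- 20 evaluable patients are needed, and for this purpose "both patients with an ovarian and endometrial malignancy, planned for a staging laparotomy can and will be included".
- Benign cases drop out: "patients with a benign result on frozen section of the suspicious ovary will be excluded from the study".
- The malignancy rate, from retrospective data, is that "in 60% of the patients with a suspicious ovary, frozen section will confirm a ovarian malignancy".
- For the false negative endpoint, "at least 10 patients with ovarian cancer should be part of the 20 evaluable patients".

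No formula is shown, and no planned number of endometrial patients is given.

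Two other places govern accrual. Section 3 says "The study will end after 20 patients, of which at least 10 patients with ovarian cancer" have completed the procedure. Section 5, on withdrawal and replacement, covers women with a benign frozen section as well as other withdrawals: "These patients will be replaced by a new study subject until 20 completed sentinel node procedures are performed".

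The surgical procedure for suspected ovarian tumours fixes the order of events: "before starting with removal of the enlarged and suspicious adnex, blue dye and the radioactive isotope will be injected". The frozen section result comes afterwards.

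**The concern.** The section presents the total as a calculation from listed inputs, so a reader can check whether the inputs give that total. They do not give it for the mixes that the protocol permits. The number of ovarian cancers has a floor of 10 and no stated expectation above it, and the total depends directly on that number.

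At stake is the count of women exposed, not the analysis. Every inclusion beyond 20 is a woman who does not complete the procedure. On the protocol's inputs, this is a woman whose frozen section is benign. She is injected with dye and radioactive tracer and undergoes the waiting time, but has no node resected and adds nothing to the detection rate. Anyone who weighs the burden of the study, or its estimated two-year inclusion period, relies on this total.

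**Working it through.** **Inputs**, all from the sample size section: malignancy rate 0.60; 20 evaluable patients; x ovarian cancers among them, x at least 10; benign cases not evaluable. Assumptions added here: no other withdrawals, endometrial patients always evaluable, independent frozen section results, x fixed in advance.

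**Can the stated range be reproduced?** Adding 40% to the ovarian number gives both ends: 10 × 1.4 + 10 = 24 and 20 × 1.4 = 28. That inflation fits a malignancy rate of 10/14 = 71%, not 60%. As no formula is shown, this origin is only a guess. The upper end also results from correct division at x = 12, since 12/0.6 + 8 = 28.

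**Expected total.** To obtain x cancers at a rate of 0.60, x/0.6 women with a suspicious ovary are needed on average. The expected total is therefore x/0.6 + (20 - x), and the expected number of benign frozen sections is that total minus 20.

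| Ovarian cancers x | Endometrial | x/0.6 | Expected total | Expected benign | P(total > 28) |
|---|---|---|---|---|---|
| 10 | 10 | 16.7 | 26.7 | 6.7 | 26% |
| 12 | 8 | 20.0 | 28.0 | 8.0 | 40% |
| 15 | 5 | 25.0 | 30.0 | 10.0 | 61% |

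**Probabilities.** A total of N or fewer suffices if N - (20 - x) women with a suspicious ovary yield at least x cancers. This is a binomial tail with rate 0.60.

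- x = 10, N = 24: at least 10 of 14, probability 0.279.
- x = 10, N = 28: at least 10 of 18, probability 0.737, so 0.263 above 28.
- x = 12, N = 28: at least 12 of 20, so 0.404 above 28.
- x = 15, N = 28: at least 15 of 23, probability 0.388, so 0.612 above 28.

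**The lower end.** Setting x/0.6 + (20 - x) = 24 gives x = 6 (6/0.6 + 14 = 24), below the floor of 10.

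**The upper end.** An expected total of at most 28 requires x × (0.4/0.6) ≤ 8, that is x ≤ 12.

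**Where the total falls at the minimum mix (x = 10).** The probability is 17% below 24, 57% from 24 to 28 and 26% above 28. The standard deviation is √(10 × 0.4)/0.6 = 3.3, and the mean excess over 28 is 0.8 patients.

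**Totals that hold with about 90% probability.** At x = 10, 30 gives 0.872 and 31 gives 0.915. At x = 15, 34 gives 0.864 and 35 gives 0.903.

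**The case against.** The best defence is that the range works for the only mix the protocol pins down. At 10 ovarian and 10 endometrial patients the expectation of 26.7 lies inside 24 to 28, and the range is the most likely outcome at 57%. The expected 6.7 benign cases also fall within the 4 to 8 that the range implies. A range normally has its lower end below the mean, and a total below 24 has a 17% chance, so 24 is a plausible low outcome. Accrual with replacement then secures the 20 procedures whatever the total turns out to be.

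Much of this stands. A reader might infer that the whole range is too low; at 10 to 12 ovarian cancers that is not so, because the expectation is still covered. A reader might also infer that the study would fall short of 20 evaluable patients; the stopping and replacement rules rule that out. Nor can it be said that the authors added 40% by mistake, because the working is not shown and 28 has another possible source. Totals for nearly all-ovarian mixes would look worse, but the protocol does not plan such a mix and says that both groups will be included.

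One part does not stand. If 24 to 28 is meant as a spread of likely totals, it is exceeded about one time in four even at the most favourable permitted mix, before any withdrawal. If it is meant as expected totals over permitted mixes, 24 belongs to none of them. On neither reading is the mix stated.

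**Conclusion.** A real but minor inconsistency. At 60% malignant, 24 inclusions are fewer than expected at every permitted mix, with only a 28% chance of reaching 10 ovarian cancers alongside 10 endometrial patients. The upper figure of 28 is enough on average only up to 12 ovarian cancers. The shortfall is small near the minimum mix and grows with the ovarian share: at 15 ovarian cancers the expected total is 2 above the upper end, with 10 benign cases expected against at most 8 implied.

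The result rests on the protocol's 60%, for which no sample size or uncertainty is given, and on no other losses. Any withdrawal raises the totals. The evaluable number and the analyses are unaffected; the consequence is an understated number of women who receive tracer and have no node resected.

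**What to change.** Keep the target of 20 evaluable patients with at least 10 ovarian cancers. State the assumed mix and restate the total to match, for example: about 27 inclusions expected with 10 ovarian and 10 endometrial patients (up to about 31 with 90% probability), and about 30 with 15 ovarian cancers (up to about 35), before withdrawals. Add that about 7 to 10 women are expected to have a benign frozen section.

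This is a change of text in one section. The target, the accrual and replacement rules and the procedures stay as they are. The only cost is a somewhat higher stated number of women included.

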### Objective:

- 1) To determine whether or not a sentinel node procedure in patients with ovarian cancer is feasible when the tracers are injected in the ovarian ligaments.
- 2) To determine the anatomical localisations of the sentinel nodes.
- 3) To determine the incidence of false negative sentinel nodes.

**Study design:** phase I feasibility study.

**Study population:** the following patients will be included:

- Patients with a high suspicion of an ovarian malignancy in whom a median laparotomy and a frozen section analysis is planned.
- Patients with endometrial cancer in whom a staging laparotomy is planned.

**Intervention (if applicable):** After opening the abdomen, before starting the surgical staging procedure, blue dye and the radioactive-colloid will be injected in the ligamentum ovarium proprium and the ligamentum infundibulo-pelvicum. This will be done on the ovary with suspicion of malignancy (patients with an ovarian tumour) or one of the normal ovaries (patients with endometrial cancer).

**Main study parameters:** percentage of patients in whom it is feasible to identify sentinel nodes. Other study parameters are the anatomical localisation of the sentinel node(s) and the incidence of false negative lymph nodes.

**Nature and extent of the burden and risks associated with participation, benefit and group relatedness:** the surgery is prolonged with 20-25 minutes due to the required

incubation time after injection of the blue dye and radioactive isotope. A scintigram will be performed 24 hours after the surgery to determine whether residual radioactive lymph nodes

can be detected. The scintigram will only be performed if the patient is capable to be transported to the nuclear department. No extra blood samples will be taken, no extra visits, physical examinations or other tests are necessary. There is no risk of tumour dissemination by injecting the tracers in the ovarian ligaments. There is a 0,07 to 2,7% risk of an allergic reaction to the blue dye. The dose of radioactive isotope given does not give adverse side effects, either to the patients or the personnel present in the operating theatre.

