### ***Background***

EOC can metastasize through three different ways [3,4]: intraperitoneal (in the abdominal cavity), lymphogenous and haematogenous. Concerning the lymphogenous spread, it is clear that lymphatic metastases of EOC mainly occur in the para-aortic lymph nodes [5]. It is believed that the tumour cells follow the lymph vessels that accompany the ovarian artery and vein in the infundibulopelvic ligament up to the high para-aortic region and renal vein. Nevertheless, pelvic lymph node metastases are also frequently found [6-16]. These tumour cells probably follow a different route, following the para-uterine vessels in the broad ligament towards the uterine artery and vein and further on to the iliac vessels. In some case reports isolated inguinal node metastases are also described [17-20]. The exact mechanism of this route of metastasis is still unclear, but the metastatic cells might follow the course of the round ligament towards the inguinal lymph nodes, or might follow the iliac vessels towards the femoral vessels. The incidence of lymph node metastasis in clinical stage I-II ovarian carcinoma is 14.2% [21].

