### ***The clinical significance of staging***

According to the International Federation of Gynecology and Obstetrics (FIGO), EOC with lymph node metastases is classified as FIGO stage IIIC disease, even in the absence of peritoneal metastases [22]. In contrast to patients with FIGO stage I ovarian cancer after a comprehensive staging procedure, patients with a FIGO stage III ovarian cancer obtain adjuvant chemotherapy. Therefore, the recognition of lymph node metastases is of utmost importance.

Surgical staging of EOC and the extent of lymph node dissection differs greatly from centre to centre [23].

A review published in 2011 showed an incidence of 14.2% for lymphnode metastasis in early EOC [21]. The incidence is higher in the grade 3 tumours (20.0%) and the serous histological subtype (23.3%). Whereas in grade 1 and mucinous tumours this is respectively 4.0% and 2.6%.

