### ***Secondary study parameters***

In order to test the reliability of the sentinel node detection by injection in the ovarian ligaments, some secondary study parameters are also important:

- The anatomical location(s) and number of the sentinel node(s), visualized at surgery by either blue dye or the radioactive tracer
- The incidence of false negative lymph nodes, i.e. in contrast to the sentinel lymph node, one of the resected non-sentinel lymph nodes contains tumor cells. To calculate the percentage of false negative lymph nodes: the number of patients with negative sentinel lymph node(s) AND positive non-sentinel lymph node(s) is the numerator, the true amount of negative lymph nodes is the denominator."

The golden standard would be to perform a complete pelvic and para-aortic lymphadenectomy. However, the Dutch guideline advises a comprehensive lymph node sampling as standard treatment. We feel such a golden standard can be considered in subsequent study, when this study provides evidence that a sentinel node procedure in this way indeed is feasible. Nevertheless, a possible false negative result obtained in this study is important and therefore will be documented.

- The incidence of unrecognized sentinel nodes

Recognition of sentinel nodes with blue dye and the gamma probe during surgery is less reliable than by making a scintigram. Therefore ideally, as in breast and vulvar cancer, a scintigram is made before surgery to recognize the sentinel nodes so that during surgery no sentinel nodes will be missed. However, this principle cannot be accomplished in patients with ovarian cancer, because the tracers cannot be injected at the appropriate sides without opening the abdomen. However, we expect that missing sentinel nodes in patients with ovarian cancer occurs less frequent because the area where the sentinel nodes can reside is restricted to well described areas. Nevertheless, by making a scintigram 24 hours after surgery, at least an impression is obtained on the incidence of unrecognized sentinel lymph nodes.

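### The minimum of 10 ovarian cancers is justified only by the false-negative endpoint, yet at the protocol's own 14.2% nodal rate it yields about 1.4 patients in whom a false negative could occur

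*Protocol*

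**What the plan says.** In the Protocol, section 4, Sample size calculation, the case-mix floor is that "at least 10 patients with ovarian cancer should be part of the 20 evaluable patients". Its purpose is given in the same bullet: "to calculate one of the secondary endpoints (incidence of false negative sentinel lymph node". No assumed rate, precision or derivation accompanies it. Section 3 (Study design) repeats the floor as part of the rule for ending the study.

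The Summary, under Objective, lists as its third item: "To determine the incidence of false negative sentinel nodes".

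Section 5, Secondary study parameters, defines the quantity: "the number of patients with negative sentinel lymph node(s) AND positive non-sentinel lymph node(s) is the numerator". The denominator is given as the truly negative nodes. The same section accepts that sampling is not the reference standard, leaves full lymphadenectomy to a later study, and says that any false negative will be documented.

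On how often nodes are involved, section 1 (Background) states: "The incidence of lymph node metastasis in clinical stage I-II ovarian carcinoma is 14.2"%. The section on the clinical significance of staging adds the subgroups: "The incidence is higher in the grade 3 tumours (20.0%) and the serous histological subtype (23.3"%), and "Whereas in grade 1 and mucinous tumours this is respectively 4.0% and 2.6"%. The sample size section uses none of these rates.

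**The concern.** By the protocol's own definition a false negative needs a metastasis in a non-sentinel node, so node-negative patients carry no information on whether the procedure misses disease. The number that matters for this endpoint is therefore the number of node-positive ovarian cancers, not the number of ovarian cancers. The protocol quotes the rate needed to work that out but does not apply it, and it ties the floor of 10 to an endpoint that 10 patients can barely inform.

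At stake is what the trial may conclude. The rationale for the procedure is that a negative sentinel node could spare a patient radical lymphadenectomy. A false-negative figure resting on zero, one or two node-positive patients says almost nothing about that.

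**Working it through.** **Inputs.** Floor of 10 ovarian cancers among 20 evaluable patients, 60% malignancy at frozen section, 24 to 28 inclusions (section 4). Nodal rate 14.2%, with subgroup rates 20.0% (grade 3), 23.3% (serous), 4.0% (grade 1) and 2.6% (mucinous) (section 1).

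**The plan's own figures.** The total can be reproduced: 10 / 0.60 = 16.7 patients with a suspicious ovary, plus 10 endometrial cancers, gives 26.7, so 27, which lies within 24 to 28. The floor of 10 has no stated derivation, so there is nothing to reproduce for it.

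**Node-positive patients among 10.** The expected number is 10 × p, P(none) = (1 − p)^10, and P(at most one) = (1 − p)^10 + 10 p (1 − p)^9. At p = 0.142:
- expected: 10 × 0.142 = 1.42
- P(none) = 0.858^10 = 21.6%
- P(at most one) = 57.4%

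| Nodal rate | Expected of 10 | P(none) | P(at most one) |
|---|---|---|---|
| 2.6% | 0.26 | 76.8% | 97.4% |
| 4.0% | 0.40 | 66.5% | 94.2% |
| 14.2% | 1.42 | 21.6% | 57.4% |
| 20.0% | 2.00 | 10.7% | 37.6% |
| 23.3% | 2.33 | 7.0% | 28.5% |

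Even if all 20 evaluable patients had ovarian cancer, only 20 × 0.142 = 2.84 would be expected to be node-positive. An expectation of five would take 5 / 0.142 = 35.2, so 36 ovarian cancers.

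**Precision, node-positive patients as denominator.** With no false negatives among n, the exact (Clopper-Pearson) 95% upper limit is 1 − 0.025^(1/n).
- 0 of 1: 97.5%
- 0 of 2: 1 − 0.025^(1/2) = 84.2%

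**Precision, the protocol's denominator.** Read per patient (an assumption, since the text counts patients in the numerator and nodes in the denominator), about 10 − 1.42 = 8.58, say 9, are true negatives. The upper limit for 0 of 9 is 1 − 0.025^(1/9) = 33.6%. With no node-positive patient at all, this definition returns 0 of 10, that is 0%, while giving no information on missed metastases. At 14.2% that happens in about one study in five.

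**Effect of non-detection.** A false negative also requires a detected sentinel node. The protocol stops only if detection is below 50%. If patients without a detected node count as evaluable (an assumption), 50% detection leaves 1.42 × 0.5 = 0.71 informative patients.

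**The case against.** **The text sets a floor and makes no promise.** It asks for a minimum number of ovarian cancers and claims no precision, power or confidence limit. A reader might infer that the protocol declares 10 patients sufficient for a reliable estimate, or that it has miscalculated something. Neither is supported: no sufficiency statement exists and no stated figure is computed wrongly. What stands is narrower: the only purpose given for the number is one that the number does not serve.

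**14.2% may not be the enrolled rate.** It belongs to clinical stage I-II disease, while the inclusion and exclusion criteria set no stage limit, and the introduction says that about 75% of patients present at advanced stage. This is a fair limit on the figures. The rationale is early-stage staging, so 14.2% is a reasonable assumption, but it is an assumption. The documents give no nodal rate for advanced disease. Taking 50% purely for illustration, five of 10 would be node-positive, and 0 of 5 still has an upper limit of 52.2%.

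**The 84% limit uses a denominator that the protocol does not use.** This is correct, and it is why both limits are shown. With true negatives below the line a percentage can always be computed, and 34% is far from 84%. The numerator, however, can still come only from the few node-positive patients.

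**The limitation is already conceded.** The study is a feasibility study, its statistics section is descriptive, no decision rests on this endpoint, and section 5 speaks of documenting false negatives. That lowers the severity. But the concession in section 5 concerns sampling as the reference standard, not the scarcity of node-positive patients, and the Summary and section 4 keep the stronger verbs.

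**Conclusion.** Wrong as written, at low severity. The floor of 10 ovarian cancers does not deliver its one stated purpose. Assuming 14.2%, it yields about 1.4 node-positive patients, with a 22% chance of none and a 57% chance of at most one; the protocol's highest quoted rate raises the expectation only to 2.3. The false-negative incidence cannot be estimated usefully under either denominator.

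The figures rest on three assumptions: the stage I-II rate applies to the patients enrolled, the ovarian group is at its minimum of 10, and the protocol's denominator is read per patient.

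Two stronger readings go beyond the documents. One is that the trial will present zero false negatives as reassurance; nothing in the protocol says so, and it is only a risk of the present wording. The other is that the study is too small for its primary aim; this point does not touch the detection rate or the total of 20. Nor is the absence of a planned confidence interval a fault here, since that may properly sit in the statistical analysis plan.

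**What to change.** 1. Section 4: keep the minimum of 10 ovarian cancers, but give its reason as observing sentinel node detection in the target disease. Add that, at 14.2%, about one to two node-positive ovarian patients are expected.
2. Section 4 and Summary: replace the verbs *calculate* and *determine* for this endpoint with *document*, in line with section 5.
3. Section 5: report false negatives as a count over node-positive patients with a detected sentinel node, in place of the true-negative denominator.
4. State that no conclusion on the accuracy of the sentinel node will be drawn from this study.

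The cost is wording in three places, including a changed endpoint definition in section 5, and a less favourable claim. It needs no extra patients and changes no procedure, sample size or primary analysis.
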